Due to the problem of attrition in the control group, it has been suggested in the last International Myopia Conference that controlled field studies be performed by a virtual group, without performing a non-inferiority study, since atropine 0.01% could not be taken as gold standard because it is not yet approved and as we said, it is off-label in Argentina. Data on progression in Asia or Europe could be used for this virtual control group, but it would be more convenient to have a virtual control group in one's own living environment. In the case of our country there is already a possible control group of 114 children of 12 years of age on average who were followed up with cycloplegia during the years pre-pandemic and from which it is known that the progression was from 0.43+/-0.52 diopters in one year.³⁶

It is thus proposed to perform a prospective clinical study in 100 children who will be enrolled when in the usual consultation for their eyeglasses control they can choose to do the treatment accessible in our environment (the diluted atropine drop) or a treatment that is possibly equally effective with special glasses designed in our environment. It is

expected that there will be similarity of effect on progression because the lens is based on the principles of defocusing of eyeglasses and contact lenses already proven by the international industry.³⁷ Our lens has the characteristic of being much simpler in its carving and construction, making it more economical for our environment where it has already been presented from the theoretical point of view.³⁸

Moreover, the special myopia control spectacle lacks the possible toxic effects of a drop instilled in the eye for many years until emerging adulthood. In addition, to avoid including children who may have rapid progressions to high myopia, treatment will be offered only to children over 8 years of age. In our environment, where children are outdoors a lot, the progression is slower than in Asian countries and is around -0.50 diopters per year, as we said.³⁶ A strong myopia is the one that exceeds -5.00 diopters.³⁹ Thus the risk for a child included in this project is to progress -0.25 diopters in six months (the resolution limit of the measurement method), so each child who does not respond well with arrest of progression at six months may be removed from the protocol and switched to atropine treatment.

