ophthalmology offices that are members of the research team. The opticians and ophthalmologists will be asked to watch a video on myopia control developed by the principal investigators where this treatment methodology is explained during the evaluation process at the center of care. The opticians will verify the optical centration in the frames chosen ad hoc, with a modern digital centration system provided by the sponsors. After 15 days, when the glasses with the correct centering are ready, the subjects will go to the optician's office to try on the glasses in that room. On this occasion, as always in these cases, the optician will evaluate the subject's adaptation and mobility in the optician's shop, instructing the child to wear the glasses at home for a couple of days and then to wear them for as long as possible.

SAMPLE AND SAMPLE SIZE

The sample size will be 50 subjects of both genders to compare with the studies abroad that consist of an n between 40 and 90 subjects and the natural history in our country that counted 114 subjects. There will be a group of subjects who will be treated with the nationally designed defocus glasses. Statistical calculation for a difference of 0.25 diopters in progression with respect to controls, for a standard deviation of 0.50 diopters gives an $n = 31$ subjects and taking into account a 20% loss to follow-up the n should equal 38 subjects in the group. Thus reaching 50 subjects exceeds expectations.

METHODS

This field study to test tolerance and percentage of effectiveness of defocus lenses in the control of myopia will include boys and girls from 8 to 15 years of age who voluntarily

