All the data of affiliation, contact telephone number, date of birth, refraction under cycloplegia, axillary length and questionnaire will be entered in a centralized digital history by NOVAR developers. These data will be kept confidential. During follow-up visits, accredited professionals throughout the country will have access to upload the data required for each visit. One month after the eyeglasses are delivered, the professional will conduct a telephone survey to parents to evaluate adherence. The first stage of the study will be completed after one year and the child will be able to continue with the treatment for myopia control according to the consensus guidelines on myopia treatment of the Myopia Study Group of the SAOI (Annex I). For virtual control group, data will be taken from 114 children followed with cycloplegia by the pandemic study group during the years 2018-2019 that showed for an average age of 12 years an annual pre-pandemic progression of -0.45 D. In the present study, We expect to evaluate the progression with peripheral defocus treatment over one year of an equivalent group of children.

WORK PLANNING / GANTT CHART:

Activity	TIME IN MONTHS						
	1	2-4	5-24	25	26	27	28
Project Design	X	X					
Bibliographic search	X			X	X		
Ethics Committee Presentation		X					
Data collection			X				
Data analysis				X	X		
Preliminary results					X	X	
Final Results						X	X
Report writing							X

INCLUSION / EXCLUSION CRITERIA

All consecutive patients of both genders who freely opt for lenses of national industry will be included in the present study. All patients who present any systemic or ocular pathology that may affect their refraction measurements or their evolution will be excluded from the study. Also excluded from the protocol in the follow-up will be those patients who, even using defocus glasses, had in 6 months an improvement equal to that expected without any intervention. These patients will be treated with other options available in our environment at the time of the change. The computerized medical records system will be configured to detect such patients at the time of loading the follow-up data and will send an alert to the investigators.

EVALUATION OF TOLERANCE AND ADHERENCE

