One month after the delivery of the spectacle, the principal investigator in charge will make a telephone call to the parent of the study subject conducting the tolerance survey and thus verifying adherence to spectacle use. The survey is detailed in the attached medical record and responses will be uploaded into the computerised web-based system that will be developed for this study. The system will automate the alerts for these safety calls with automatic emails sent to the principal investigator in the month of spectacle delivery.

PLAN FOR ANALYSING THE RESULTS

The results of numerical variables shall be expressed as mean and standard deviation or median and interquartile range according to whether they are normally or skewed. Nominal variables will be expressed as absolute frequency and percentage. For the comparison of numerical variables, Student's t-test or Mann Whitney U-test will be used as appropriate. Nominal variables will be compared using the Chi-square test or Fisher's exact test as appropriate. A p-value of $p \leq 0,05$.

HUMAN RESOURCES

[name] and [name] are in charge of the design and control of the research. Statistical analysis will be performed by [name]. Physicians accredited to treat patients will have to demonstrate the ability to perform routine consultations for myopia control, refraction studies under cycloplegia and optical biometry. Once accredited, they will have a username and password to upload their data into the web form. Accredited doctors will be in permanent communication with doctors [name] and [name]. There will be a myopia progression monitoring system within the computerised system that will send reports if any child progresses more than 0.25 dioptres in six months to alert researchers so that precautionary measures can be taken in such cases.

MATERIAL RESOURCES

Optotypes, Retinoscope, Autorefractometer and Biometer posters of accredited institutions.

Approximately four institutions with a high turnover of paediatric consultations are expected to be accredited for an estimated enrolment time of 6 months.

Peripheral defocus spectacles will be provided by the sponsor (NOVAR) free of charge to all study subjects for one calendar year with the possibility of extending the study for two years. At the end of the study, if the expected positive results are found, the glasses will remain in the possession of the study subjects.

FINANCIAL RESOURCES

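### The sample size allows for 20% loss but not for the six-month removals, and comparing only the children who remain with the 114 controls would favour the lens

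*Combined protocol and SAP*

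**What the plan says.** All references are to the combined protocol and SAP.

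- **SAMPLE AND SAMPLE SIZE.** "Statistical calculation for a difference of 0.25 diopters in progression with respect to controls, for a standard deviation of 0.50 diopters gives an" n of 31; then "taking into account a 20% loss to follow-up the n should equal 38 subjects in the group". Planned enrolment is 50, and the section ends "Thus reaching 50 subjects exceeds expectations".
- **INCLUSION / EXCLUSION CRITERIA.** "Also excluded from the protocol in the follow-up will be those patients who", despite wearing the glasses, "had in 6 months an improvement equal to that expected without any intervention". They move to other treatment. I read this as progression at or above the untreated rate.
- **CURRENT STATE OF RESEARCH.** The wording is permissive: "each child who does not respond well with arrest of progression at six months may be removed from the protocol". The same paragraph gives 0.25 D in six months as the risk to a child.
- **HUMAN RESOURCES.** The monitoring system will "send reports if any child progresses more than 0.25 dioptres in six months". This is an alert, not a removal rule.
- **METHODS.** The virtual control group is 114 children with "an annual pre-pandemic progression of -0.45 D". No six-month removal is described for them.
- **PLAN FOR ANALYSING THE RESULTS.** It lists t-test or Mann-Whitney and chi-square or Fisher. It names no analysis set and gives no handling for removed children.
- **EVALUATION OF TOLERANCE AND ADHERENCE.** Adherence is reported as the number of enrolled children who do not complete all three visits. Tolerance and adherence are also graded good or bad from a questionnaire.

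**The concern.** Removal at six months is a second route out of the one-year comparison, separate from loss to follow-up, and the sample-size section leaves it out. Two things are at stake for efficacy, the secondary objective but the only one for which a sample size is calculated.

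The first is the number of children with a one-year value on the spectacles. The second, and larger, is that removal depends on the outcome itself. The children who progress fastest in the first half-year leave the treated group, while their counterparts stay among the controls. A comparison of those who remain then credits the lens with the effect of the selection, and more enrolment does not cure it.

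The primary objective is touched as well. Unless 12-month visits continue after removal, a removed child is counted as an adherence failure, which mixes non-response with non-adherence.

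**Working it through.** **The plan's own figures.** With two-sided 5% and 80% power (neither is stated; they are assumed because they fit), a one-sample formula gives n = (0.50 × 2.80 / 0.25)² = 31.4, so 31 reproduces. For the loss, 31 × 1.20 = 37.2, rounded up to 38. Dividing instead, 31 / 0.80 = 38.75, or 39. I take 31 as given.

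**Inputs.** Effect 0.25 D and one-year SD 0.50 D (sample-size section); controls 0.45 D per year (METHODS). The six-month limit L is 0.45 / 2 = 0.225 D under the exclusion criteria, or 0.25 D as in CURRENT STATE OF RESEARCH. **Assumed:** normal change, and a six-month SD s from 0.25 D (steady rate, 0.50 / 2) to 0.354 D (independent half-years, 0.50 / √2).

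**Share removed** = 1 − Φ((L − m/2)/s), with m the true yearly change on the lens. If the lens works, m = 0.45 − 0.25 = 0.20 and m/2 = 0.10.

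| L (D) | s (D) | Removed | Left of 50, no other loss | Left of 40, after 20% loss |
|---|---|---|---|---|
| 0.25 | 0.25 | 27.4% | 36.3 | 29.0 |
| 0.225 | 0.25 | 30.9% | 34.6 | 27.7 |
| 0.25 | 0.354 | 33.6% | 33.2 | 26.6 |
| 0.225 | 0.354 | 36.2% | 31.9 | 25.5 |

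After 20% loss, the count reaches 31 when removal is 1 − 31/40 = 22.5%. Without other loss, 50 children tolerate 1 − 31/50 = 38%.

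**Bias if only remaining children are analysed.** With z = (L − m/2)/s, their mean yearly change is m − (0.125/s) × φ(z)/Φ(z). The 0.125 is the covariance of six-month and one-year change; it is the same in both scenarios (0.25 × 0.50, and 0.50²/2). For a lens with no effect, m = 0.45:

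| L (D) | s (D) | Removed | Mean of remaining (D) | False benefit (D) |
|---|---|---|---|---|
| 0.225 | 0.25 | 50.0% | 0.051 | 0.399 |
| 0.25 | 0.25 | 46.0% | 0.082 | 0.368 |
| 0.225 | 0.354 | 50.0% | 0.168 | 0.282 |
| 0.25 | 0.354 | 47.2% | 0.184 | 0.266 |

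If the lens works, the same selection turns a true 0.25 D into an apparent 0.44–0.51 D. In simulated trials (50 enrolled, 20% lost, 114 controls, two-sided 5% t-test), a lens with no effect is declared beneficial in about 63–98% of trials, against a nominal 2.5%. Analysing all 40 brings this back to about 2.5%.

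**Milder readings.**

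- Half of the flagged children removed: 33–35 left if the lens works; false benefit 0.09–0.13 D if it does not.
- Removal only from 0.375 D (above 0.25 D, recorded in 0.25 D steps): 14–22% removed and 31–35 left if the lens works. If it does not, false benefit is 0.19–0.23 D, declared in about 43–65% of trials.

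**Other direction.** A six-month SD of 0.50 D would give 38–40% removed and 24–25 left.

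**The case against.** The strongest reply is that the shortfall is a scenario, not the plan's arithmetic. That stands. The figures 31 and 38 reproduce, the six-month SD is my assumption, and the limit and control rate come from other sections. A reader might infer that 50 children cannot deliver 31. The documents do not support that: removal alone leaves 32–36 of 50. Falling below 31 needs mandatory removal at 0.225–0.25 D, further loss on top, and no one-year data from removed children. The three wordings of the rule disagree, and on the milder readings the shortfall goes.

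A reader might also infer that a useless lens must appear to gain at least the 0.25 D the study is sized for. That is not established. The milder readings give 0.09–0.23 D. Allowing for an assumed measurement error of 0.20–0.25 D per reading within the 0.50 D SD brings the full-removal figure to about 0.22–0.29 D. The bias also arises only if remaining children alone are compared, which the plan does not specify. But nor does it exclude this, and it provides no one-year value for a removed child.

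A third inference, that visit completion is capped at 64–73%, fails too. The three yearly consultations are described as routine under FINANCIAL RESOURCES, so a removed child may still attend at 12 months, and the questionnaire grades adherence separately.

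Finally, CURRENT STATE OF RESEARCH speaks of 100 children. If all wore the lens, 51–58 would remain on the full-removal assumptions, with the same bias.

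**Conclusion.** The point holds in a conditional form and should be fixed. The sample size omits an outcome-dependent removal that the plan itself states, and the analysis plan does not say what happens to those children.

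On numbers, about 27–36% removed and 26–29 left of 50 is plausible under normal change, a six-month SD of 0.25–0.354 D, a true 0.25 D effect, full removal and a separate 20% loss. On milder readings about 31–35 remain.

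On bias, the conclusion does not depend on the count of 31. On every reading examined, comparing only the remaining children favours the lens: by about 0.27–0.40 D for a lens with no effect under full removal, and 0.09–0.23 D otherwise. A positive result from that comparison could not be told apart from selection.

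**What to change.** **SAMPLE AND SAMPLE SIZE.** State that the 20% does not include six-month removals, give the expected evaluable number as a range with its assumptions, and delete the closing sentence that 50 is more than expected. Enrolment can stay at 50.

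**PLAN FOR ANALYSING THE RESULTS.** Add: *One-year progression is analysed in all children who received the spectacles. Children removed at six months still have the 12-month refraction recorded at the routine visit and are included regardless of later treatment. A repeated-measures model that keeps the six-month change and estimates the 12-month change on spectacles is a supporting analysis, with its extrapolation stated. An analysis of the remaining children alone is not used to claim efficacy.*

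**EVALUATION OF TOLERANCE AND ADHERENCE.** Report six-month removals separately from missed visits.

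**Removal wording.** CURRENT STATE OF RESEARCH, INCLUSION / EXCLUSION CRITERIA and HUMAN RESOURCES must be reconciled on who is removed and whether removal is optional. No clinical rule is proposed here.

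**Cost.** Wording in three sections and one extra model. No visits are added, since three consultations a year are already routine.

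**Downside, to be stated in the plan.** The main comparison includes any effect of the later treatment. As an illustration, suppose it cut second-half progression by 60%, the figure the background gives for atropine. A lens with no effect would then gain from 0.472 × 0.60 × 0.225 = 0.06 D (independent half-years) to 0.50 × 0.60 × 0.424 = 0.13 D (steady rate, where removed children average 0.225 + 0.25 × 0.798 = 0.424 D per half-year). That is well below 0.27–0.40 D but not zero, so both analyses should be shown side by side.

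The supporting model extrapolates above the removal cut-off. In simulation its power at 0.25 D is about 55–76%, against 77% if all 40 had a one-year value on spectacles, and it declares false benefit in 2.6–4.4% of trials (nominal 2.5%).

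### The sample-size figures do not fit together: 38 misses the plan's own 31 after 20% loss, 31 matches no declared test against the 114 controls, and enrolment is both 100 and 50

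*Combined protocol and SAP*

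**What the plan says.** In SAMPLE AND SAMPLE SIZE, "The sample size will be 50 subjects of both genders". The basis is "Statistical calculation for a difference of 0.25 diopters in progression with respect to controls, for a standard deviation of 0.50 diopters", which is said to give n = 31. The section continues: "taking into account a 20% loss to follow-up the n should equal 38 subjects in the group. Thus reaching 50 subjects exceeds expectations". It states no power, no sidedness and no test.

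The comparator is a virtual control group. In METHODS, "data will be taken from 114 children followed with cycloplegia by the pandemic study group". CURRENT STATE OF RESEARCH gives that group's spread: "it is known that the progression was from 0.43+/-0.52 diopters in one year".

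For numerical variables, PLAN FOR ANALYSING THE RESULTS says Student's "t-test or Mann Whitney U-test will be used as appropriate", with a threshold of p ≤ 0.05. Sidedness is again not given.

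CURRENT STATE OF RESEARCH also proposes a study of 100 children, who may choose between diluted atropine and the special glasses. METHODS mentions a contrast-reduction lens for some children and gives no number for that group. OBJECTIVES makes tolerance and adherence primary and control of progression secondary.

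**The concern.** The closing statement of the sample-size section tells the reader that 50 children are more than enough. Whether that is so depends on which test the 31 came from, and the plan does not say. The calculations that yield 31 at conventional 80% power are not a two-sided comparison with a sample of 114, which is the ordinary reading of a t-test or Mann-Whitney test at p ≤ 0.05. The step from 31 to 38 also fails on the plan's own figures, and the total of 50 stands beside an unreconciled 100.

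At stake is whether a reader can tell what difference the 50 children can detect, and how many of them contribute to the defocus-lens comparison. If sidedness stays open, it could also be settled after the data are seen.

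**Working it through.** **Inputs from the plan.** Difference δ = 0.25 D, SD σ = 0.50 D, n = 31, loss 20%, inflated n = 38 and enrolment 50 (SAMPLE AND SAMPLE SIZE). Controls m = 114 (same section and METHODS). Control SD 0.52 D (CURRENT STATE OF RESEARCH). Level 5% (PLAN FOR ANALYSING THE RESULTS).

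**Assumption.** Power of 80%, because the plan states none. The normal quantiles are 1.960 (two-sided 5%), 1.645 (one-sided 5%), 0.842 (80%) and 0.524 (70%).

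**Step 1: reproduce n = 31.** For a one-sample test, n₁ = [σ(z_α + z_power)/δ]². For a two-sample test against a fixed m = 114, 1/n = 1/n₁ − 1/114.

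| Test | Power | n |
|---|---|---|
| One-sample, two-sided | 80% | (2 × 2.802)² = 31.4 |
| One-sample, one-sided | 80% | (2 × 2.486)² = 24.7 |
| Two-sample v 114, one-sided | 80% | 1/(1/24.73 − 1/114) = 31.6 |
| Two-sample v 114, two-sided | 80% | 1/(1/31.40 − 1/114) = 43.3 |
| Two-sample v 114, two-sided | 70% | n₁ = (2 × 2.484)² = 24.7, so n = 31.5 |

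Three rows come to about 31. The one-sample row treats the control mean as known. The one-sided row needs a test that the plan does not declare. The two-sided comparison with the 114 reaches 31 only at about 70% power. At 80% it needs 44 children by the normal formula, or 45 by the noncentral t (44 gives 79.95%).

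**Step 2: the allowance for loss.**
- 38 × 0.8 = 30.4, which is below 31.
- 31/0.8 = 38.75, so 39 are needed; 39 × 0.8 = 31.2.
- 31 × 1.2 = 37.2, rounded up, is 38. The stated figure is consistent with multiplying by 1.2 instead of dividing by 0.8.

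**Step 3: power of the 50.** Completers are 50 × 0.8 = 40. The standard error is 0.50 × √(1/40 + 1/114) = 0.0919 D, and 0.25/0.0919 = 2.72.

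| Test at 40 completers | Normal formula | Noncentral t |
|---|---|---|
| Two-sided v 114, SD 0.50 | Φ(2.72 − 1.96) = 77.7% | 77.1% |
| Two-sided v 114, SD 0.52 in both groups | 74.4% | 73.9% |
| One-sided v 114, SD 0.50 | 85.9% | 85.6% |
| One-sample, two-sided, SD 0.50 | 88.5% | 86.9% |

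The difference detectable with 80% two-sided power against the 114 is 2.802 × 0.0919 = 0.257 D, or 0.259 D by the noncentral t: about 0.26 D.

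**Step 4: enrolment.** CURRENT STATE OF RESEARCH says 100 and SAMPLE AND SAMPLE SIZE says 50. No section relates the two.

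**The case against.** The strongest reply is that 80% is not the plan's figure. The plan states no power, and 70% two-sided against the 114 also gives 31.5. On that reading 40 completers give 77%, above target, and 50 is indeed more than required. Under the two readings that give 31 at 80%, the 40 completers have about 86% to 87%. It can also be said that the closing sentence claims only that 50 exceeds 38, which is true and would be true of 39. All of this stands as far as it goes: no shortfall is proven. It does not rescue the text, because 70% is no more declared than a one-sided test is, and the reader is assured that 50 is ample without being told for which comparison.

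Three stronger readings are tempting, and the documents do not support them.

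- **Six-month removals as further lost power.** CURRENT STATE OF RESEARCH says "each child who does not respond well with arrest of progression at six months may be removed from the protocol", and INCLUSION / EXCLUSION CRITERIA says "Also excluded from the protocol in the follow-up will be those patients who, even using defocus glasses, had in 6 months an improvement"; the benchmark there is the untreated course. A reader might treat these children as extra dropout and quote a lower power. But they leave because of poor response, so the loss is not random. A comparison restricted to completers would be biased in favour of the lens, and a reduced power figure would hide that.
- **A smaller defocus group.** A reader might infer from the contrast-reduction lens that only part of the 50 wear defocus lenses. The sample-size section speaks only of a defocus-glasses group, and no split is given, so a power for any assumed split has no basis.
- **An inflated false-positive rate.** Treating the mean of the 114 as known would raise the error rate of a one-sample test. But the plan takes data from the 114 children and names Mann-Whitney, a two-sample test, so nothing shows that the one-sample analysis is intended.

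**Conclusion.** The point holds as an inconsistency in the stated figures, not as a finding that the trial is too small.

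- **38 should be 39.** This follows from the plan's own numbers and needs no assumption. It has no practical consequence, since 50 are planned.
- **The adequacy of 50 is unsupported if the comparison with the 114 is two-sided and 80% is the target.** Power is then about 77% at SD 0.50 D and 74% at SD 0.52 D in both groups. That is roughly 3 to 6 points short, or, at SD 0.50 D, 0.26 D in place of 0.25 D. A one-sided test would have about 86%. These figures assume 40 completers, random loss, and the 114 entering as a sample. The gap concerns the secondary objective only.
- **100 and 50 are unreconciled.** The 100 may be all the children offered the choice of treatment, but no section says so.

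**What to change.** Edit SAMPLE AND SAMPLE SIZE, and the sentence in CURRENT STATE OF RESEARCH that gives 100.

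1. Change 38 to 39, or delete it.
2. Replace the closing assurance with the power of the planned comparison. For example: *Against the 114 controls, at a two-sided 5% level, 40 completers of 50 enrolled give about 77% power for 0.25 D at SD 0.50 D (74% at SD 0.52 D in both groups), or 80% power for 0.26 D.* If a one-sided test was intended, declare it before analysis and state about 86% instead.
3. Give one enrolment target, say how 100 relates to 50, and state how many of the 50 are defocus-lens children.

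Do not add reduced power figures for children removed at six months; that is a question of bias for the analysis.

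The cost is a few sentences, with no extra children, visits or budget. If the test is two-sided, the power on paper becomes slightly less favourable than the present text suggests.
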